3.5 Patient disposition

Patient disposition for all randomized patients will be summarized based on the FAS. There will be one combined by-treatment summary showing:

1. Number (%) of patients treated/untreated
2. Number (%) of patients who are still on-treatment (based on the absence of the ‘End of treatment’ page)
3. Number (%) of patients who discontinued study treatment (based on the ‘End of Treatment’ page)
4. Reasons for study treatment discontinuation (based on ‘End of Treatment’ page)
5. Number (%) of patients who entered the post-treatment evaluations (based on ‘End of Treatment’ page)
6. Number (%) of patients who discontinued from the post-treatment evaluations (based on ‘End of post treatment follow up disposition’ page)
7. Reasons for discontinuation from the post-treatment evaluations phase (based on ‘End of post treatment follow up disposition’ page)
8. Number (%) of patients who entered survival follow-up.

In a separate summary, the reasons for patients not completing the screening phase will be presented based on the “Screening Phase Disposition” CRF.

3.6 Study treatment

Duration of study treatment exposure, cumulative dose, dose intensity (DI) and relative dose intensity (RDI) will be summarized by treatment. The number of patients with dose reductions/interruptions, and the reasons, will be summarized and listed. Details of the derivations and summaries are provided in the following sections.

The safety set will be used for all summaries and listings of study treatment.

3.6.1 Duration of study treatment exposure

The duration of exposure to study treatment will be calculated as

Duration of exposure to study treatment (days) = (*last date of exposure* to any study treatment component) – (date of first administration of study treatment) + 1.

Duration of exposure to any single component of study treatment will be calculated as

Duration of exposure (days) = (last date of exposure to study treatment component) – (date of first administration of study treatment component) + 1.

The *last date of exposure* is defined as follows for the study treatment components:

- For ribociclib/placebo, tamoxifen, anastrozole, and letrozole: the last date of exposure is defined as the date of last administration of the corresponding medication;

- For goserelin, the last date of exposure is defined as the date of last administration of goserelin + 27 days.
 - If a patient died or was lost to follow-up within date of last administration + 27 days, then the last date of exposure is the date of death or last contact date, respectively.

This duration of exposure includes the periods of temporary interruption (of any component of the study treatment for any reason). The duration of study treatment exposure and exposure to each treatment component will be summarized by treatment arm. In addition, the duration of exposure will be categorized into time intervals (e.g. <3 months; 3-<6 months; 6-<9 months, etc); frequency counts and percentages will be presented for the number of patients in each interval.

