### 6.1.1 Dosing regimen

LEE011 or LEE011 placebo will be given orally once daily on days 1-21 of each 28 day cycle. Days 22-28 will be a “rest” period from dosing with LEE011 or LEE011 placebo. Tamoxifen, letrozole, and anastrozole will be given orally once daily on a continuous daily schedule (e.g., days 1-28 of each 28 day cycle). Goserelin will be given as an injectable subcutaneous implant on day 1 of every 28 day cycle. There will be no “rest” in the tamoxifen, letrozole, or anastrozole schedule.

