2.1.9 Last contact date

For patients not known to have died at the analysis cut-off the last contact date will be derived using the last complete date among the following:

Table 2-1 Last contact date data sources

Source data	Conditions
Date of Randomization	No Condition
Last date patient was known to be alive from Survival Follow-up page	Patient status is reported to be alive, lost to follow-up or unknown.
Start/End dates from further antineoplastic therapy	Non-missing medication/procedure term.
Start/End dates from drug administration record	Non-missing dose. Doses of 0 are allowed.
Date of discontinuation/study phase completion from end of treatment or end of post-treatment follow-up disposition page	No condition.
Date of ECG assessment	At least one non-missing parameter value
Date of PRO assessment	At least one non-missing answer to questionnaire
Tumor (RECIST) assessment date	For non-target lesion: non-missing lesion status For target lesion: non-missing lesion diameter For new lesion: "Is there a new lesion?" = yes
Laboratory collection dates	At least one non-missing parameter value
	
Vital signs date	At least one non-missing parameter value

Source data	Conditions
Performance Status date	Non-missing performance status
Start/End dates of AE	Non-missing verbatim term
Concomitant medication date	Non-missing medication
████████████████████	██
Body fluid/Tissue Collection/Results	Non-missing result (positive/negative tumor cells)
██	██
Cardiac imaging date	Non-missing LVEF or overall interpretation

The last contact date is defined as the latest complete date from the above list on or before the data cut-off date. The cut-off date will not be used for last contact date, unless the patient was seen or contacted on that date. No date post cut-off date will be used. Completely imputed dates (e.g. the analysis cut-off date programmatically imputed to replace the missing end date of a dose administration record) will not be used to derive the last contact date. For patients who died, the last contact date is defined as the date of death. Partial date imputation is allowed for event (death)/censoring from the ‘Survival information’ eCRF.

The last contact date will be used for censoring of patients in the analysis of overall survival.

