2.2 Data included in the analysis

The primary PFS endpoint will be carried out after approximately 329 PFS events have been documented based on local assessment, and up to 3 analyses for OS may be performed as described in [Section 3.8.2.1](#).

For each of the analyses, cutoff dates will be established and statistical analyses will be performed using all data collected in the database up to the data cutoff date. Any data collected beyond the cutoff date will not be included in the analysis and will not be used for any derivations.

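### The goserelin exposure end date (last injection + 27 days) is not capped at the data cut-off, so exposure of patients still on treatment runs up to 27 days past it

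*SAP*

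**What the plan says.** In the primary-analysis SAP, 3.6.1, exposure to study treatment runs from the first administration to the last date of exposure to any component. For ribociclib/placebo, tamoxifen, anastrozole and letrozole, "the last date of exposure is defined as the date of last administration of the corresponding medication". Goserelin is treated differently: "For goserelin, the last date of exposure is defined as the date of last administration of goserelin + 27 days". One sub-rule shortens that date: "If a patient died or was lost to follow-up within date of last administration + 27 days", the date of death or the last contact date is used instead. The data cut-off is not mentioned.

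The same section says "The duration of study treatment exposure and exposure to each treatment component will be summarized by treatment arm", and it also asks for counts in 3-month intervals. The final-CSR SAP, 3.5.1, carries the same goserelin rule with the same two exceptions, and uses the same calculation for exposure in the cross-over period.

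Two other places bear on the question. SAP 2.2 says "Any data collected beyond the cutoff date will not be included in the analysis and will not be used for any derivations". SAP 2.1.9 mentions, as an example of a fully imputed date, "the analysis cut-off date programmatically imputed to replace the missing end date of a dose administration record". The schedule is in Protocol 6.1.1: "Goserelin will be given as an injectable subcutaneous implant on day 1 of every 28 day cycle".

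**The concern.** The added 27 days are reasonable in themselves, because one implant covers a 28-day interval. The difficulty is with patients still on treatment at the cut-off. Their tablets end on or before that date, but the goserelin date is projected forward and normally falls after it. Because overall exposure takes the latest component date, the projected date becomes the end of study treatment exposure too.

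The exceptions for death and loss to follow-up suggest that exposure was meant to stop where observation stops. The commonest way for observation to stop, the administrative cut-off, is missing. Elsewhere the same SAP does apply this kind of cap:

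- The censoring date for time to first laboratory toxicity (3.9.2) is the earliest of several dates, among them end of treatment + 30 days and the analysis cut-off.
- The last contact date (2.1.9) may not be later than the cut-off.
- An imputed death date (3.8.2.1) uses the smaller of last contact + 1 day and the cut-off.

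At stake is the accuracy of the goserelin and overall exposure summaries and their 3-month categories.

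**Working it through.** The documents give no exposure figure that this rule should produce, so there is none to reproduce. The check is date arithmetic, followed by an illustration of size.

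**One patient.** Let k be the number of days from the last injection to the cut-off. On a 28-day schedule k runs from 0 to 27. Days credited after the cut-off = 27 − k. This is positive for k = 0 to 26, which is 27 of the 28 positions. The maximum is 27 days (27/30.4375 = 0.89 months). The mean over the 28 positions is 13.5 days (0.44 months).

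**A category shift.** Take injections on days 1, 29, …, 253 and a cut-off on day 258.
- SAP rule: 253 + 27 = day 280, or 280/30.4375 = 9.20 months, in the interval starting at 9 months.
- Capped at the cut-off: 258 days, or 8.48 months, in the 6 to <9 month interval.
- Difference: 22 days and one category.

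**Does SAP 2.2 already prevent this?** It bars data collected after the cut-off. The injection was collected before the cut-off, and the end date is calculated forward from it. No later data are used, so the rule does not bite. The imputation mentioned in 2.1.9 closes an open dosing record at the cut-off, but says nothing about the 27 days added to an injection date.

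**Arm level.** Neither SAP gives the share of patients on treatment at the primary cut-off. As a proxy I use the design PFS assumptions (SAP 3.16): control median 9 months, hazard ratio 0.67, uniform accrual over 18 months, cut-off at 22 months. Follow-up is then uniform on 4 to 22 months, and the share still event-free is

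p = [exp(−4λ) − exp(−22λ)] / (18λ), with λ = ln 2 / median.

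| | Control | Ribociclib |
|---|---|---|
| Median (months) | 9 | 9/0.67 = 13.4 |
| λ per month | 0.0770 | 0.0516 |
| p | 0.398 | 0.530 |
| Excess, p × 13.5 (days) | 5.4 | 7.2 |
| Excess (months) | 0.18 | 0.24 |
| Mean to last treated day, (1 − p)/λ (months) | 7.82 | 9.11 |
| SAP rule, adding 0.44 (months) | 8.27 | 9.55 |
| Capped, SAP rule minus excess (months) | 8.09 | 9.32 |
| Excess relative to capped mean | 2.2% | 2.5% |

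The 0.44 months is added to every patient because those who have stopped also receive the tail. If the share on treatment is instead taken anywhere from 10% to 75%, the arm-level excess is 1.4 to 10.1 days.

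**Dose intensity.** The goserelin formula (SAP 3.6.3) carries its own + 27 days. For 12 injections on a perfect schedule it gives 3.6 × 12 / (336/28) = 3.6 mg/28 days, as it should. If that denominator were capped with the cut-off on the day of the twelfth injection, the result would be 43.2 / (309/28) = 3.91, above the planned intensity. That formula should be left alone.

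**The case against.** The strongest reply is that the 27 days are a coverage convention. The implant releases drug throughout the cycle, the injection itself was observed, and the dose-intensity formula uses the same convention. SAP 2.1.8 also says that treatment duration follows different rules from the on-treatment window. This explains the 27 days. It does not explain why the tail is cut at last contact for a patient lost to follow-up but not at the cut-off for a patient still being followed.

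A second reply is that the cap may sit in the programming dataset specifications, which are not among the documents. That is possible, but the SAP as written gives the uncapped date, and SAP 2.2 does not correct it.

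Two stronger readings are tempting, and the documents do not support either.

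- A reader might infer that the rule favours the ribociclib arm. The difference of about 1.8 days (7.2 − 5.4) appears only when exposure is compared with the capped quantity. Measured from the last treated day, the SAP rule adds about 13.6 days in both arms under the same scenario, while the capped rule adds about 8.2 days in control and 6.4 in ribociclib. The asymmetry depends on the benchmark chosen.
- A reader might infer that the reading of adverse events is distorted. AE summaries are numbers and percentages of patients (SAP 3.9.1.3), and their window ends 30 days after the last administration (2.1.8), not at this exposure date. Neither SAP specifies an exposure-adjusted rate. Ribociclib/placebo exposure, the component that differs between the arms, is summarized separately and ends at the last administration.

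It is also fair to say that the effect is small, and that the number ongoing at the final-CSR cut-off is unknown. Amendment 7 records 114 of 672 patients on treatment on 8 January 2020. At that share the mean excess would be about 114/672 × 13.5 = 2.3 days.

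**Conclusion.** The point holds as a minor error in a derivation rule. For patients still on treatment, the rule as written gives goserelin and overall study treatment exposure an end date up to 27 days after the data cut-off, about 13 days on average. At the primary analysis the mean overstatement is about 5 days in control and 7 in ribociclib, roughly 2%, with some patients moved to a higher 3-month category.

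The per-patient figures rest only on the 28-day schedule and an even spread of injections around the cut-off. The arm-level figures rest on PFS as a stand-in for time on treatment. Patients also stop for toxicity or by choice, so the share ongoing may be lower.

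Nothing inferential is affected, and neither are the separate durations of the oral components, any dose intensity or the AE counts.

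**What to change.** In the primary-analysis SAP, 3.6.1, define the goserelin last exposure date as the earliest of:

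- last administration + 27 days;
- date of death;
- last contact date, if the patient is lost to follow-up;
- the data cut-off date.

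Make the same change in the final-CSR SAP, 3.5.1, where it matters for any patients still on treatment at that cut-off. Leave the goserelin dose-intensity formula in both SAPs as it is. If the programming specifications already apply the cap, the added wording brings the SAP into line with them.

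The cost is one phrase in each SAP and, if the cap is not already programmed, one line of code. Reported mean exposure would become about 2% shorter at the primary analysis under the assumptions above.

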3.6.2 Cumulative dose and average daily dose

Cumulative dose for any component of study treatment is defined as the total dose of the medication given during the study treatment exposure.

Average daily dose is defined as [Cumulative dose (mg) / Number of dosing days]; drug free day(s) are not counted as dosing days.

Cumulative dose and average daily dose will be summarized using descriptive statistics by treatment arm for each component of study treatment. Patients with no exposure to the study treatment component will be excluded from the corresponding summary.

3.6.3 Dose intensity and relative dose intensity

Dose intensity (DI) for patients with non-zero duration of exposure to each study treatment component is defined as follows:

For tamoxifen, letrozole, and anastrozole, DI is defined as

DI (mg/day) = Cumulative dose (mg) / duration of exposure to study treatment component (days).

For goserelin, DI is defined as

DI (mg/28 days) = Cumulative dose (mg) / {[(date of last administration of goserelin + 27) – (date of first administration of goserelin) + 1] / 28},

to account for the goserelin dosing schedule in the DI computation.

For ribociclib/placebo, DI is defined as

DI (mg/day) = Cumulative dose (mg) / *adjusted* duration of exposure to ribociclib/placebo (days),

where *adjusted* duration of exposure (days) to ribociclib/placebo represents the number of ribociclib/placebo dosing days a patient would be expected to have received per protocol, given their duration of exposure to ribociclib/placebo as defined in [Section 3.6.1](#). Since ribociclib/Placebo follows a 3 weeks on, 1 week off schedule, the adjusted duration of exposure to ribociclib/placebo is the duration of exposure to ribociclib/placebo minus the planned off days. The adjusted duration of exposure to ribociclib/placebo is therefore 21 x (# completed 28 day cycles) + min(21, duration of last incomplete cycle).

For example, if the duration of exposure to ribociclib/placebo is 66 (corresponding to two cycles and 10 days), then the adjusted duration of exposure to ribociclib/placebo is $21 \times 2 + 10 = 52$. If the duration of exposure to ribociclib/placebo is 108 days (corresponding to three cycles and 24 days), then the adjusted duration of exposure is $21 \times 3 + 21 = 84$ days.

Specifically, let D1 represent the duration of exposure to ribociclib/placebo as defined in [Section 3.6.1](#). Then the adjusted duration of exposure is defined as

$$D = 21 \times [D1/28] + \min(21, D1 - 28 \times [D1/28]) \text{ days,}$$

where [x] stands for the integer part of x. In this equation $[D1/28]$ is the number of completed cycles, and $D1 - 28 \times [D1/28]$ is the additional number of days in the last, incomplete cycle (if any). For example, if $D1 = 30$ then $[D1/28] = 1$, $D1 - 28 \times [D1/28] = 2$, and $D = 23$. If $D1 = 7$ then $D = 7$; if $D1 = 22$ then $D = 21$; if $D1 = 28$ then $D = 21$, etc.

Planned dose intensity (PDI) is defined as the assigned dose by unit of time planned to be given to patients as per protocol. The PDI for each study treatment component is displayed in [Table 3-1](#). Note that DI will also be calculated and reported in the units displayed in [Table 3-1](#), whereas duration of exposure itself will be summarized in months.

Table 3-1 Planned dose intensity

Medication	PDI (dose unit/unit of time)
Ribociclib/placebo	600 mg/day
Tamoxifen	20 mg/day
Letrozole	2.5 mg/day
Anastrozole	1 mg/day
Goserelin	3.6 mg/28 days

Relative dose intensity (RDI) is defined as:

$$RDI = DI \text{ (dosing unit / unit of time) } / PDI \text{ (dosing unit / unit of time).}$$

DI and RDI will be summarized separately for each of the study treatment components.

3.6.4 Dose reductions, interruptions and delays

The number and percentage of patients with dose reductions, interruptions or delays, and the reasons, will be summarized by treatment arm as outlined below.

Interruption: An interruption is defined as a 0mg dose given on one or more days during the period where (for ribociclib/placebo only) a patient is not on the “off” part of a treatment cycle, after which > 0mg dose resumes. For patients who had dose interruption checked but never resumed non-zero dose, the dose interruption will not be counted. For example, in the sequence of 600 mg – 0mg (dose break) -0mg (dose interruption) – 0 mg (dose permanently discontinued) the 0mg (dose interruption) will not be counted as a dose interruption. Interruptions will be summarized for each component of study treatment.

Delay: A special case of an interruption is one that, for ribociclib/placebo, occurs at the start of a new cycle, after a planned rest period. Such instances will be identified as a subset of the interruptions (specifically those occurring directly after a planned dose break) and will be summarized separately as dose delays.

Reduction: A dose reduction for ribociclib/placebo is defined as a decrease from the previous non-zero dose to another non-zero dose less than the protocol-planned dose, even if this decrease has been directly preceded by an interruption. For example, in the sequence 600mg – 0mg – 400mg, the 400mg dose will be counted as a reduction.

If due to dosing error, a patient took a dose during the dosing break with a dose that is lower than the previous dose, this will not be considered as a dose reduction. For example, a patient took 600 mg from day 1-21, then mistakenly took 200 mg per day on day 22-28, which is supposed to be a dosing break, then resumed 600 mg dosing on day 29. This will not be considered as a dose reduction.

Missing data: If dose is recorded but frequency is missing or entered as ‘none’, it is assumed that the study drug was taken as per-protocol.

In this study, dose reductions for letrozole, anastrozole, tamoxifen or goserelin are not permitted and will not be summarized, however all dosing data will be listed.

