## **10.3 Treatments (study treatment, concomitant therapies, compliance)**

The safety set will be used for the analyses below.

The actual dose and duration of tamoxifen/NSAI, goserelin, LEE011 and placebo treatment, as well as dose intensity (computed as the ratio of actual dose received to actual duration) and the relative dose intensity (computed as the ratio of the dose intensity to planned dose received/planned duration), will be listed and summarized using descriptive statistics. The total daily doses of tamoxifen/NSAI, goserelin, LEE011 and placebo for each patient will be summarized using descriptive statistics (e.g. mean, median, and mode).

Concomitant medications and significant non-drug therapies will be listed by patient and summarized by ATC (Anatomical therapeutic chemical classification system) term for each treatment group. These summaries will include medications starting on or after the start of study treatment or medications starting prior to the start of study treatment and continuing after the start of study treatment. Any prior concomitant medications or significant non-drug therapies starting and ending prior to the start of study treatment will be listed.

Compliance to the study drug will be assessed by the number of dose reductions and dose interruptions.

The duration of exposure to study treatment and each component of study treatment will also be summarized for the crossover phase in patients who crossed over to LEE011 combination therapy after unblinding (i.e. using the Crossover analysis set).

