#### **10.5.3.6 Tolerability**

Tolerability will be studied in terms of dose reductions and drug interruptions due to AE. Reasons for dose reductions and interruptions will be listed and summarized by treatment.

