3.6.5 Discontinuation of study treatment components

The reasons for discontinuation of each study treatment component will be summarized by treatment arm, based on the information on the component-specific DAR CRFs (i.e. using the “Reason Dose Permanently Discontinued” field on the applicable DAR CRF for patients who have the “dose permanently discontinued” box checked).

Partial discontinuation: Partial discontinuations and their reasons will also be summarized for ribociclib/placebo and goserelin (separately). Partial discontinuation refers to discontinuation of ribociclib/placebo or goserelin, respectively, while continuing on study treatment.

- For ribociclib/placebo, partial discontinuation is defined as the event when the last non-zero dose of ribociclib/placebo is more than 21 days before the last non-zero dose of study treatment, with the permanent discontinuation box checked in the ribociclib/placebo DAR page;
- For goserelin, partial discontinuation is defined as the last non-zero dose of goserelin plus 27 days being more than 21 days before the last non-zero dose of study treatment, with the permanent discontinuation box checked on the goserelin DAR page.

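### The SAP's dose-interruption count excludes holds still open at the data cut-off, so a patient whose only hold is open is summarised as neither interrupted nor discontinued in the dosing tables

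*SAP*

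**What the plan says.** Section 3.6.4 of the primary-analysis SAP defines an interruption as a 0 mg dose on one or more days outside the planned off period, "after which > 0mg dose resumes". It then makes the exclusion explicit: "For patients who had dose interruption checked but never resumed non-zero dose, the dose interruption will not be counted". Its single illustration is a planned break, then a flagged interruption, then a permanent stop, where "the 0mg (dose interruption) will not be counted as a dose interruption". Delays at the start of a cycle are treated as a subset of interruptions, so they inherit the condition. Section 3.5.4 of the final-CSR SAP carries the same exclusion.

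Three other rules decide where a patient on hold is placed:

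- Discontinuation of a component (primary-analysis SAP 3.6.5) is taken from the reason field "on the applicable DAR CRF for patients who have the “dose permanently discontinued” box checked".
- Section 2.2 states: "Any data collected beyond the cutoff date will not be included in the analysis and will not be used for any derivations".
- The disposition table in section 3.5 has a row for the "Number (%) of patients who are still on-treatment (based on the absence of the" End of treatment page).

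The final-CSR SAP has equivalent rules in 3.5.5, 2.2 and 3.4.

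The protocol attaches no resumption condition to either use of interruptions. Section 10.3 says "Compliance to the study drug will be assessed by the number of dose reductions and dose interruptions", and section 10.5.3.6 says "Tolerability will be studied in terms of dose reductions and drug interruptions due to AE".

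**The concern.** The rule has a sensible purpose in the case it illustrates: one continuous stop should not be reported both as an interruption and as a discontinuation. The sentence is not limited to that case. It also removes a hold that has not ended by the cut-off, where there is no discontinuation to report instead. Such a patient is known to be off drug on planned dosing days, yet the dosing summaries present her as on treatment without interruption.

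At stake is the accuracy of the number and percentage of patients interrupted or delayed, with reasons. The protocol relies on this measure for compliance and, where adverse events are the cause, for tolerability. The error runs in one direction, and a long hold is more likely than a short one to be open on any given cut-off date.

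**Working it through.** The documents state no interruption count or rate to reproduce. The check is to apply the rules to dose sequences, starting with the SAP's own example.

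**Rules applied.** A recorded interruption is counted only if a dose above 0 mg appears later in the data up to the cut-off (3.6.4 and 2.2). A patient is discontinued from the component only if the permanent-discontinuation box is ticked (3.6.5).

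| Ribociclib sequence up to cut-off | Recorded | Counted by SAP | In interruption summary | In discontinuation summary |
|---|---|---|---|---|
| SAP example: 600 mg, planned break, interruption, permanent stop | 1 | 0 | no | yes |
| 600 mg, planned break, 600 mg, interruption open at cut-off | 1 | 0 | no | **no** |
| 600 mg, interruption, 600 mg, interruption open at cut-off | 2 | 1 | yes | no |
| 600 mg, interruption, 400 mg | 1 | 1 | yes | no |

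Row 1 reproduces the SAP's stated outcome. Row 2 is the gap. Row 3 shows that the patient-level count is unchanged if an earlier hold resumed; only the episode is lost.

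**Does dose intensity show the hold instead?** Section 3.6.3 gives the adjusted exposure D = 21 × [D1/28] + min(21, D1 − 28 × [D1/28]). This reproduces the SAP's own figures: D1 = 66 gives 21 × 2 + 10 = 52, and D1 = 108 gives 21 × 3 + 21 = 84. Exposure ends at the last administered dose (3.6.1). Take two full cycles followed by a hold over all of cycle 3:

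- The last dose is on day 49, so D = 21 + 21 = 42. The cumulative dose is 42 × 600 = 25,200 mg, and relative dose intensity is 25,200 / 42 / 600 = 100%.
- Had the 21 missed dosing days been included, D would be 63, giving 25,200 / 63 / 600 = 67%.

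Relative dose intensity therefore does not reveal an open hold either.

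**Size.** The share of patients on hold at a cut-off is not given. The following is an illustration only:

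- Patients on treatment in the ribociclib arm: 89 (3 July 2019, Amendment 6) or 79 (8 January 2020, Amendment 7).
- Patients per arm: about 672 / 2 = 336, assuming an even split.
- Assumed: 2% to 10% of those on treatment are on hold, and 0% to 50% of these have an earlier hold that resumed.
- Missed patients = number on treatment × share on hold × (1 − share with an earlier resumed hold).
- Low end: 79 × 0.02 × 0.5 = 0.8 patient, or 0.8 / 336 = 0.2 percentage point.
- High end: 89 × 0.10 × 1 = 8.9 patients, or 8.9 / 336 = 2.6 percentage points (2.65 before rounding).

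The number on treatment at the primary-analysis cut-off is not in the documents, so this range does not transfer to that report.

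**The case against.** The strongest reply is that little is hidden. Adverse events requiring treatment interruption are tabulated by system organ class, preferred term and grade (primary-analysis SAP 3.9.1.4; final-CSR SAP 3.7.1.4). The adverse event form records temporary interruption as an action taken (Protocol 8.1.1), and no resumption condition is stated for those tables. The protocol's tolerability measure is limited to interruptions due to adverse events, which are the holds these tables keep. The primary-analysis SAP also lists interruptions with reasons and all dosing data. A reader might infer that a patient on hold is counted nowhere; the documents do not support that. What remains is narrower. A hold for another reason, open at the cut-off, is in no specified summary, and the final-CSR SAP specifies dosing listings only for the cross-over set.

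A reader might also infer that holds ending in permanent discontinuation are lost. They are not: the SAP's example shows that they are deliberately reported as discontinuations, with the stopping reason. A toxicity hold followed by stopping for progression does lose its own reason in the dosing tables, but an adverse event recorded with temporary interruption as the action taken stays in the adverse event table. The protocol does not define an interruption, so this is a legitimate convention.

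A third tempting reading is that the undercount is known to be larger on ribociclib. That is a reasonable expectation, since the protocol requires holds for several toxicities, but no figure in the documents establishes it. Nor is it a defect that the dosing and adverse event tables may differ, because they draw on different sources.

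None of this covers the open hold, which the exclusion removes without reclassifying it.

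**Conclusion.** The point stands in a limited form. Under the rules as written, a patient whose only hold is open at the cut-off is absent from both the interruption and the component-discontinuation summaries. The reported number and percentage of patients interrupted or delayed can only be too low. The patient-level count falls only where no earlier hold resumed.

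The magnitude cannot be derived from the documents; the 0.2 to 2.6 points above rest on assumed hold shares. The consequence is confined to descriptive dosing summaries. PFS, OS, adverse event incidence and discontinuation counts are unaffected. For the final report the effect should be small if few patients are still on treatment at its cut-off.

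**What to change.** In primary-analysis SAP 3.6.4 and final-CSR SAP 3.5.4:

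- Restrict the exclusion to a hold followed by a ticked permanent discontinuation of that component, which is the case the example describes.
- Count a hold that is open at the cut-off and outside the planned off days as an interruption (or a delay, where that definition applies), with its recorded reason, and show it in a separate row for holds ongoing at the cut-off.

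In the table above, row 1 would stay at 0, row 2 would change from 0 to 1, row 3 from 1 to 2, and row 4 would stay at 1. Holds that end in permanent discontinuation need no change.

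The cost is one sentence and one derivation in each SAP, and a slightly higher reported interruption rate. The separate row lets a reader recover the count under the present rule.
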